## **Study Protocol**

### *Trial design*

A care provider and participants blinded, parallel, randomized controlled trial with three groups was completed from September 2022 to April 2023. This trial is reported according to the CONSORT 2010 checklist for randomized controlled trials. All procedures were approved by the Ethics Committee of the Polytechnic Institute of Coimbra (CEIPC 6/2022).

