### *Outcomes and testing procedures*

Before (T0) and after 12-weeks (T1) of interventions and control procedures, concentric and eccentric peak torque (PT) of IR and ER of the dominant and non-dominant shoulder was performed through an isokinetic dynamometer Biodex System 3 (Biodex Medical Systems, New York), at 60°/s, 120°/s and 180°/s.

Previously to strength evaluations, each swimmer did a 10-minute warm-up of a general upper limb joint mobilization. The isokinetic dynamometer assessment was carried out with the swimmer in the supine position. Half of the swimmers started the assessment with the dominant shoulder, and the other half started with the non-dominant shoulder. Previously, this order was randomized for each swimmer. The upper extremity was positioned with the shoulder abducted to 90° and the elbow flexed to 90° so that the dynamometer's axis was aligned with the longitudinal axis of the humerus. The athlete's trunk and evaluated arm were stabilized using velcro straps to avoid compensatory movements (Fig. 3). Gravity correction was not used for this testing position because the ER and IR shoulder muscles moved with and against gravity as they applied force. Strength was tested through 145° of range of motion (ROM), between 80° of ER and 65° of IR, to obtain the PT variation in the maximum rotational ROM available. The tests started every time with the shoulder in 80° of ER. The concentric strength was tested first, followed by the eccentric strength test. The order of the angular velocity test was increased (60°/s-120°/s-180°/s) to preserve an ascending difficulty during the evaluations. A hard cushion deceleration control was selected to allow the subject the greatest availability of velocity attainment before deceleration. The procedure was explained to all athletes before the start of testing, with emphasis on exerting maximal effort within an individual's tolerance. After this, swimmers performed 3 submaximal trials to familiarize themselves with the ROM and the accommodating resistance of the dynamometer. Both concentric and eccentric tests at different velocities consisted of 5 maximal-effort reciprocal repetitions. Standardized verbal instructions and encouragement were given to all subjects. A minute rest period between different tests was preserved.

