### *Randomisation and blinding*

An initial screen survey was carried out on the two swimming teams before the sample selection. After the application of eligibility criteria, the eligible swimmers were divided into a weight program group, an elastic band program group, or a control group. The allocation to each group was performed through stratified randomization according to the team, sex, and main swimming style. This design was used to equate the possible effects of these three variables in results and was prepared with a computer random number generator by a member of the research team. Then, all swimmers carried out the T0 assessment moment through the isokinetic dynamometer. To minimize fatigue bias during the assessments, half of the swimmers started the evaluation with the dominant shoulder, and the other half started with the non-dominant shoulder. Previously, this order was randomized for each swimmer. After T0 moment, for 12-weeks the two experimental interventions were applied and supervised by a blinded sports physiotherapist external to the study, without knowledge of the previous procedures and the study objectives. It only explains in detail the interventions and the load that should be used by each athlete considering the 1RM test previously performed by a member of the research team. The participants were unaware of the existence of other sample groups. At the end of the 12-weeks, all swimmers who

completed the proposed interventions carried out the T1 strength assessment through the isokinetic dynamometer. All T0 assessment procedures were maintained in T1 moment.

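### Allocation precedes the T0 strength test and no blinded outcome assessor is described, so effort-dependent peak torque could be measured at T0 and T1 by staff who know the group

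*Combined protocol and SAP*

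**What the plan says.** The Randomisation and blinding section gives the order of events. After a screening survey of the two teams, "After the application of eligibility criteria, the eligible swimmers were divided into a weight program group, an elastic band program group, or a control group", by stratified randomisation on team, sex and main swimming style. The next step is "Then, all swimmers carried out the T0 assessment moment through the isokinetic dynamometer". The interventions start after T0. The T1 test repeats the T0 procedures.

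On blinding, Trial design describes "A care provider and participants blinded, parallel, randomized controlled trial with three groups". The Randomisation and blinding section enlarges on those two parties only. The experimental programs were "supervised by a blinded sports physiotherapist external to the study, without knowledge of the previous procedures and the study objectives", and "The participants were unaware of the existence of other sample groups". No outcome assessor is named or described as blinded.

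On roles, the stratified allocation "was prepared with a computer random number generator by a member of the research team", and a research-team member, not further identified, performed the 1 RM test that sets the training load. The dynamometer operator is not identified, and no step is described that conceals the allocation until T0 is finished.

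On the measurement, Outcomes and testing procedures asks swimmers for maximal effort within their tolerance and states that "Standardized verbal instructions and encouragement were given to all subjects".

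**The concern.** A baseline taken before allocation cannot be influenced by the allocation, whoever takes it. Once the list exists first, that protection depends on the tester not knowing it, and the plan does not provide for this. T1 has the same gap, because its procedures copy those of T0.

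The dynamometer records torque objectively, but the torque produced is voluntary. A tester who knows the group can, without intending to, vary the intensity of encouragement, the strapping or the acceptance of a trial.

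Both planned analyses are exposed. The Statistical Analysis Plan tests T0 against T1 within each group, so a shift at T0 that is not repeated at T1 is read as change. It also compares the three groups at T1, so a shift at T1 is read as a group difference.

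**Working it through.** **The plan's own figure.** The Sample size section gives alpha 0.01, power 0.99 and d = 2.81, hence 8 per group and 24 in total. An exact two-sided two-sample t-test has power 0.9722 with 7 per group and 0.9903 with 8, so 3 × 8 = 24 is reproduced. It is not disputed; it supplies n = 8 below.

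**Sequence and blinding, side by side.**

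| Step | What the documents state | What they leave open |
|---|---|---|
| Allocation | After eligibility, list prepared by a research-team member | Who else saw the list, and when |
| 1 RM tests | Initial test by a research-team member; retest after 6 weeks in the two programs; no progression for controls | Timing of the initial test relative to allocation; who ran the retest |
| T0 | After allocation | Who tested; whether they knew the group |
| T1 | Same procedures as T0 | The same |

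Whoever runs the six-week retest can tell program swimmers from controls before T1, and nothing separates that role from the dynamometry.

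**Illustration for the planned paired test.** From the documents: n = 8 per group, two-sided level 0.05. Assumed, because the documents give no figure: no true effect; equal SDs at T0 and T1; measured T0 shifted by b SD in one arm, with no shift at T1; T0-T1 correlation r.

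- SD of the T0-T1 difference, in units of the outcome SD: √(2(1 − r)).
- Noncentrality: b√8 / √(2(1 − r)).
- Rejection when |t| exceeds 2.365 (7 df).

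Example, r = 0.8 and b = 0.5: SD of the difference = √0.4 = 0.632; noncentrality = 0.5 × 2.828 / 0.632 = 2.236; rejection probability 0.487.

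| r | b = 0.2 | b = 0.5 |
|---|---|---|
| 0.5 | 7.8% | 23.2% |
| 0.8 | 12.2% | 48.7% |
| 0.9 | 19.5% | 77.4% |

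The nominal rate is 5%. The rates are the same whichever way T0 is shifted: lower effort at T0 looks like a gain, higher effort like a loss.

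**Illustration for the planned T1 comparison.** A shift at T0 alone leaves this test at 5%. If the shift occurs at T1 instead:

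- Two groups: noncentrality b√(8/2) = 2b, critical value 2.145 (14 df). For b = 0.2 and 0.5 the rejection rate is 6.6% and 15.4%.
- Three-group ANOVA with both active groups shifted against control: f = b√2/3, λ = 24f² = 0.213 and 1.333, giving 6.4% and 14.7%.

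**The case against.** **The documents do not say that any tester knew the group.** This is correct. A reader might infer that T0 was run by the same people who made the list and did the 1 RM tests. The text does not support that: it mentions a research-team member for each of those two tasks, without saying whether they were the same person, and names no dynamometer operator. A list that exists is not a list that the tester has seen. What stands is that knowledge was possible and no safeguard is described.

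**Mitigations exist.** Encouragement was standardised, torque was recorded by an instrument, the starting shoulder was randomised, and swimmers did not know of other groups, so comparison with other groups could not drive their own effort. These points reduce the risk. None of them acts on a tester who knows the group.

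**The error rates rest on assumptions.** They do. The size of any shift and the correlation are not in the documents, and the paired figures require a shift at T0 that is absent at T1. An equal shift at both times cancels in the paired test, and a common proportional effect on external and internal rotation cancels in the ER:IR ratios. The figures show sensitivity; they are not estimates of bias in this trial. An inflated error rate for a between-arm comparison of change scores would be beside the point, because the Statistical Analysis Plan contains no such test.

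**Two further inferences fail.** Loss of swimmers between allocation and T0 might be suspected, but the text says that all swimmers did T0. The care-provider label might be called misleading, but the Randomisation and blinding section already defines it as not knowing the previous procedures and the study objectives, so only wording is at issue.

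**Conclusion.** The point holds as a gap in protection against assessment bias. Allocation came before T0, blinding is described for care provider and participants only, and the outcome depends on effort at both time points. It does not hold as a finding that testers knew the group or that the results are biased.

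Its possible size depends on the unknown shift and correlation. For 0.2 to 0.5 SD at T0 in one arm, 8 per group, no true effect and no matching shift at T1, the planned paired test would reject in about 8-23% of trials at r = 0.5, 12-49% at r = 0.8 and 20-77% at r = 0.9. The planned T1 between-group test is untouched by a T0 shift; a T1 shift of the same size would raise it to about 6-15%.

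**What to change.** **In the plan.** Complete T0 for every eligible swimmer and then allocate. Have T0 and T1 run by an existing team member who neither holds the allocation list nor runs the 1 RM tests. The two changes belong together: reordering protects T0 only, and T1 depends on the separation of roles. Reordering costs nothing, because all swimmers are screened before allocation and the interventions start only after T0. Separating roles costs some scheduling within the current team.

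**For this trial.** Trial design reports it as completed, so the sequence cannot be changed, and the description of it should not be rewritten as if it had been. State who ran the T0 and T1 tests and whether they knew the allocation. If they did, or if this cannot be established, qualify the within-group and the T1 between-group conclusions as resting on unblinded outcome assessment. The cost is a few sentences.

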### *Intervention programs*

Twice a week, over 12-weeks, the two intervention groups carried out a strength training program with the 5 open kinetic chain exercises most often reported in the literature to prevent swimmer's shoulder: internal rotation (IR) at 90°, external rotation (ER) at 90°, scapular punches, T's, and Y's (Table

1). The weight program group performed these 5 exercises with two weights Domyos with 1, 2, 3, 4, or 5 kg (Fig. 1), and the elastic band program group with an elastic band Bodytone Power Band with 10, 15, 20, 25, or 30 kg (Fig. 2). The load used to perform the programs with elastic bands and weights was previously assessed and adjusted for each swimmer, corresponding to 75% of one repetition maximum (1 RM). After 6 weeks of program execution, each swimmer carried out another 1 RM test assessment, to verify the possibility of a load instrument progression.

[figure not shown]
Participants performed 2 sets of 10 valid repetitions in each exercise. The repetitions were considered valid when the swimmer reached the target range of motion (ROM) previously described for each exercise (Table 1). The concentric and eccentric phases of each exercise were performed for 5 seconds. A Tabata timer mobile application controlled this time. One minute of rest was preserved between different exercises and sets.

Programs were supervised by a sport physiotherapist independent of the study. Each athlete received individualized monitoring with a regular exercise technique correction in all sessions. The first session was in person and the following sessions have online monitoring through WhatsApp Messenger or Zoom Video Communications, Inc.

| Exercise  | Weight program                                                                                                                                                           | Elastic band program                                                                                                                                                                                                      |

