### *Control group*

[figure not shown]
The control group performed a sham intervention, twice a week, for 12-weeks. This intervention consisted of 2 sets of 10 repetitions of 5 shoulder mobility exercises, without preventive aim, normally carried out in warm-up before training: shoulder maximum flexion and extension, horizontal abduction and adduction starting from 90° of shoulder abduction, maximum IR and ER starting from 90° of shoulder abduction, circumduction of the shoulder in a clockwise direction and circumduction of the shoulder in a counterclockwise direction. There was no progression after 6-weeks of this sham intervention. The coach of the respective team checked the execution of the exercises, but there was no individualized monitoring with a regular exercise technique correction by a physiotherapist.

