## **Statistical Analysis Plan**

The data was previously filtered (smoothing option) and windowed at 95% of test velocity. Data analysis was performed using the Acqknowledge 4.1 software. The mean and standard deviation (SD) of the PT assessments in the 5 repetitions of different muscles (IR and ER), actions (concentric and eccentric), and angular velocities (60°/s, 120°/s, and 180°/s) for both sides were calculated. Subsequently, the conventional concentric ER : concentric IR ratio and the functional eccentric ER : concentric IR ratio were verified for these three angular velocities.

All statistical analysis was carried out using IBM SPSS Statistics 27 software. Mean and SD were used for sample characterization. The Shapiro-Wilk test was used to verify the normality of the sample distribution. The homogeneity of variance between the three groups was verified for the sample characterization variables and the main outcome at T0, through the One-Way ANOVA or the Kruskal-Wallis tests. After this, an inter-group analysis in T0 and T1 and an intra-group analysis between T0 and T1 was made for dominant and non-dominant shoulders. For an inter-group analysis, the One-Way ANOVA or the Kruskal-Wallis tests were applied to compare differences between the three groups in T0 and T1. For an intra-group analysis, the Paired Sample T-test or the Wilcoxon test was applied to compare differences in each group between T0 and T1. A p-value  $\leq 0.05$  was considered as the level of significance for each difference in PT and ER:IR ratios.

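### T1 testing is described only for swimmers who completed their programme, so the T1 and paired comparisons probably condition on a post-randomisation event; completion is undefined and no analysis set is named

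*Combined protocol and SAP*

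**What the plan says.** The section *Randomisation and blinding* gives the sequence. Eligible swimmers are allocated to three groups, and then "all swimmers carried out the T0 assessment moment through the isokinetic dynamometer". After 12 weeks, T1 is described for those who "completed the proposed interventions carried out the T1 strength assessment through the isokinetic dynamometer".

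*Outcomes and testing procedures* places the measurements "Before (T0) and after 12-weeks (T1) of interventions and control procedures". It gives the timing but does not say which swimmers were tested.

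The *Statistical Analysis Plan* has two main comparisons. One-way ANOVA or Kruskal-Wallis tests "were applied to compare differences between the three groups in T0 and T1". Within groups, "the Paired Sample T-test or the Wilcoxon test was applied to compare differences in each group between T0 and T1". It names no analysis set and gives no rule for a swimmer with a T0 value but no T1 value.

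The arms were run differently. In the two exercise programmes, loads were set at 75% of 1 RM, and *Intervention programs* says "Each athlete received individualized monitoring with a regular exercise technique correction in all sessions". In the sham arm, which did mobility exercises checked by the team coach, *Control group* says "there was no individualized monitoring with a regular exercise technique correction by a physiotherapist".

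**The concern.** The population narrows between T0 and T1, and the condition that narrows it arises after randomisation. If T1 exists only for completers, the T1 group comparison is between those who finished one programme and those who finished another. Randomisation balances the arms as allocated; it does not balance those who remain. Each paired test likewise describes change only among those who stayed. The T0 group comparison, which supports baseline similarity, may include swimmers who are absent at T1.

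Completion could plausibly differ by arm, because a loaded, individually monitored programme and an unmonitored mobility routine may lose different swimmers. If completion depends on both arm and strength, the T1 difference mixes the effect of training with the effect of selection. Without a definition of completion, an analysis set or per-arm counts, a reader cannot tell whether this happened.

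**Working it through.** **1. The text, side by side.**

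| Question | Where | Answer |
|---|---|---|
| Who was tested at T0? | Randomisation and blinding | All swimmers, after allocation |
| Who was tested at T1? | Randomisation and blinding | Those who completed the interventions |
| When? | Outcomes and testing procedures | Before and after 12 weeks; does not say who |
| What counts as completing? | Intervention programs; Control group | Two sessions a week for 12 weeks are planned (2 x 12 = 24); no attendance threshold |
| Who is analysed? | Statistical Analysis Plan | Not stated |
| Allowance for loss? | Sample size | None stated |

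Only one sentence says who was tested at T1, and it is restricted to completers. The paired tests need both values, so they cover at most the swimmers tested at T1.

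**2. The plan's own figure.** The sample size section gives alpha 0.01, power 0.99, d = 2.81, and 8 per group (24 in total). Taking d as a between-group difference in a two-sided two-sample t-test (noncentral t), power is 0.972 with 7 per group and 0.990 with 8. The figure of 8 is reproduced and contains no allowance for loss. On the same assumption, 6 or 5 per group at T1 would give 0.926 or 0.821. At the planned effect, then, small losses leave power high, and selection is the main issue.

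**3. Size of a possible shift (illustration).** The planned 8 per arm is from the document. The number lost and the correlation are assumptions, because the documents give neither.

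Let r be the correlation, within an arm, between completing (yes/no) and T1 strength. Let p be the share kept, q = 1 - p the share lost, and SD the standard deviation of T1 strength in the whole arm.

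- For a yes/no variable: mean of kept - mean of lost = r x SD / sqrt(pq).
- Mean of kept - mean of whole arm = q x (mean of kept - mean of lost) = r x SD x sqrt(q/p) = r x SD x sqrt(lost/kept).

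With loss in one arm only, this is also the shift in the between-group difference:

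| Lost of 8 | sqrt(lost/kept) | r = 0.3 | r = 0.5 |
|---|---|---|---|
| 1 | sqrt(1/7) = 0.378 | 0.11 SD | 0.19 SD |
| 2 | sqrt(2/6) = 0.577 | 0.17 SD | 0.29 SD |

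**4. Ceiling.** Suppose exactly the weakest swimmers leave and strength is normal. The two lowest expected order statistics for n = 8 are -1.4236 and -0.8522. The shift is 1.4236/7 = 0.20 SD with one lost and (1.4236 + 0.8522)/6 = 0.38 SD with two. These correspond to r of about 0.203/0.378 = 0.54 and 0.379/0.577 = 0.66. A value of r = 0.5 is therefore strong selection, and with one lost it is close to the maximum.

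**5. Direction.** If weaker swimmers leave a programme arm, the programme-minus-control difference rises; if stronger ones leave, it falls. Loss from the control arm reverses both. If the same kind and number of swimmers leave both arms, the shifts cancel. If opposite kinds leave, they add. With no loss, the shift is zero.

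**The case against.** The strongest reply is that nothing is shown to have gone wrong. The T1 sentence can be read as saying that every swimmer completed and was tested. The outcomes section describes T0 and T1 testing without restriction. No attendance or withdrawal figures are given, and differential completion is inferred only from differences in load and supervision. The trial design section commits to CONSORT 2010 reporting, so the flow may be given in a report outside these documents.

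Much of this stands. A reader might infer that non-completers were refused T1, that swimmers were lost, or that the result is biased in favour of the programmes. The documents support none of these: no passage states an exclusion, no loss is recorded, and the sign depends on who leaves and from which arm.

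It does not remove the point. The only stated rule on who reached T1 is restricted to completers, and following it makes the T1 and paired tests conditional on completion. That is more than an omitted detail.

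It is also fair to say that an imputation exercise would be heavy. There are 2 muscles x 2 actions x 3 velocities x 2 sides = 24 peak torques, plus 2 ratios x 3 velocities x 2 sides = 12 ratios. Running it across 36 series would be out of proportion, so it is optional here.

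**Conclusion.** The concern holds in a limited form. Completers-only testing at T1 is the likelier reading, not a stated exclusion. On that reading, the T1 group comparison and the paired tests are conditional on an undefined post-randomisation event, and the SAP does not say who is analysed.

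Under the assumed losses, a shift of 0.11 to 0.29 SD in either direction is plausible when one or two of 8 leave one arm. If everyone completed, it is zero. The actual bias cannot be sized from the documents.

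It is tempting to set these shifts against the planned d of 2.81 and call them small. The sample size section does not say which contrast or measure that d describes, so no percentage is given. Reproducing 8 per group with a two-sample test does not settle this.

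**What to change.** **For a repeat of the design.** Replace the T1 sentence in *Randomisation and blinding* with: *All randomised swimmers are invited to T1 regardless of sessions completed.* State in the SAP that the main analysis includes all randomised swimmers with a T1 value, in their assigned group. Add a sensitivity analysis in completers only, with completion defined.

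**For this trial.** The trial design section says that it "was completed from September 2022 to April 2023", so the procedure must not be rewritten as if the new rule had been followed. Instead:

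1. Define completion, and say whether any non-completer was tested at T1.
2. Analyse every T1 value that exists in the assigned group. If only completers have one, this changes nothing.
3. Report per arm the numbers randomised, tested at T0 and tested at T1, with the T0 values of those lost.
4. If any were lost, state that the T1 comparison is not fully protected by randomisation. Limiting the conclusion to completers is not a remedy, because completers may differ between arms.
5. Optionally, if T1 values are missing, run a sensitivity analysis for them on one named outcome.

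**Cost.** For this trial: a definition, a short table and possibly a caveat, with no new testing. For a repeat: one extra isokinetic session per non-completer, and a possibly smaller estimated effect because partial adherers are included.
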